#### 9.13 Image Interpretation

**Anatomic imaging** will be assessed by a pediatric radiologist with expertise in abdominal imaging ([name]). The well-distended distal/terminal ileum bowel wall thickness will be measured in 3 locations, and a mean wall thickness value will be obtained on each exam. The largest visible right lower quadrant mesenteric lymph nodes will be measured in short axis on each exam. Any secondary signs of inflammation (perienteric fat stranding, engorged vasa recta, free fluid) will be documented on each exam. After completion of the primary anatomic review by [name], a second pediatric radiologist with expertise in abdominal imaging will perform the same review on a random subset of subjects in order to determine inter-reader reliability. The second reviewer will be blinded to the initial assessment as well as to the time point of imaging.

**Motility imaging** will be assessed as follows: First, a quantitative assessment will be performed. A well-distended segment of distal/terminal ileum will be chosen by the first reviewer ([name]). Novel, semi-automated software, will be utilized to assess the coronal cine sequences in this investigation. No pre-market submission to the FDA has been made for the software nor are there any current plans to do so in the future. The semi-automated method computes a cross sectional area across time and the creates a best fit curve to determine the frequency or frequencies of contraction. After reviewer 1 identifies the bowel segment of interest, a post processing assistant will draw a region of interest on the bowel lumen on every image of the sequence. The application then creates a map of luminal cross-sectional area over time. The area versus time waveforms can be submitted to secondary analysis from which contraction frequency and other quantitative metrics of interest can be extracted.

Next a qualitative assessment will be performed. The research assistant will create a movie file for each subject, randomize the timepoints, and then insert the movie file into a PowerPoint presentation. The two reviewers, along with a third reviewer (a pediatric gastroenterologist with expertise in gut motility) will review the images to determine which movie has faster motility, and for each movie, if the motility is organized or disorganized. Finally, each of the three reviewers will assess the focal segment of the distal/terminal ileum in the same manner.

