#### **a) Descriptive statistics:**

Descriptive statistics will be calculated for all demographic, anthropometric, reactogenicity, serum, image and fecal variables. For continuous variables, five-number (mean, SD, minimum, median, maximum) summaries will be produced. For class (categorical) variables, frequencies and percentages will be reported. Descriptive statistics will be calculated for the entire study population, as well as for each vaccine group at each time point. Investigators will be advised by study statisticians about potential outliers, or data entry issues, based on these summary statistics. To determine whether continuous serum, image and fecal outcomes meet the assumption of a Gaussian (normal) distribution, the Shapiro-Wilk test will be used. Where a significant departure from normality exists, an appropriate transformation of the data will be employed prior to inferential analyses. If transformations are not successful, non-parametric analyses will be used.

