**b) Inferential statistics**

The primary analysis for this study is the comparison of anatomical outcome as measured by MRI between (RV1, RV5 with and without other vaccines: 4 groups) and within (pre and post) study groups. The primary anatomical outcome will be the terminal ileum thickness measured in mm. The change in this outcome before and after vaccination will be compared for each study group (within group test) using a paired t-test, while the between group difference at pre, post and on the difference between pre and post (change score) will be initially analyzed using general linear model (GLM) where the ileum thickness (at pre, post and change score) is modeled as a function of group (4-groups). Depending on the result of the F-test from the GLM analysis, this will be followed by pairwise comparison between groups (6-comparisons). This will be examined using a two sample t-test. If the difference between groups with and without other vaccines for a given vaccine (RV1 or RV5) is not significant we might combine the categories and conduct a comparison test for the outcome between the two vaccine types. If the primary outcome is not normal before or after transformation we will use the non-parametric Kruskal-Wallis test to compare the groups. Although the primary between group comparisons is based on the pre-post change score, we are conducting additional analysis based on the pre and post data to get more insight about the distribution of the primary outcome variable.

We will also examine the distribution of socio-demographic and other potential covariates among the groups using a GLM analysis. If some covariates are differentially distributed among the groups, those covariates will be controlled for in the primary analysis described above. Potential modifiers such as breast milk or secretor status will be examined by modeling the primary outcome as a function of group, potential modifier and the interaction between group and modifier. In this case the parameter of interest is the coefficient of the interaction term, however it is possible that the interaction test might not be sensitive due to sample size. Regardless we will examine and report the observed change between groups for each potential modifier as a subgroup. For example we will report difference between groups in the primary outcome for secretors and non-secretors separately.

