### **Power**

Since sample-sizes were predetermined and since this is a pilot study, no power calculations were conducted. Effect sizes will be reported from the results, to aid in the development of future studies.

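### The radiologist whose readings form the primary MRI endpoint is not said to be masked to visit, although the reliability reader is

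*Combined protocol and SAP*

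**What the plan says.** Section 10.3 b) sets the endpoint: "The primary anatomical outcome will be the terminal ileum thickness measured in mm". Its primary analysis has a within-arm and a between-arm part. For the first, "The change in this outcome before and after vaccination will be compared for each study group (within group test) using a paired t-test"; for the second, "the primary between group comparisons is based on the pre-post change score".

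Section 9.13 gives the anatomic MRI reading to one pediatric radiologist, who measures the wall at three places on each exam and averages them. Software is described only for motility, so I take the thickness reading to be manual; the plan does not use that word. A second radiologist "will perform the same review on a random subset of subjects in order to determine inter-reader reliability", and for that person alone the section adds: "The second reviewer will be blinded to the initial assessment as well as to the time point of imaging". For the qualitative motility review, the research assistant is to "randomize the timepoints, and then insert the movie file into a PowerPoint presentation". Section 9.22 repeats the two-reader arrangement for ultrasound, which is not the primary endpoint, with the same masking sentence for the second reader only.

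The remaining masking text is in section 4.1 (imaging staff and parents, to rotavirus vaccine type) and section 10.1 (parents and all study radiologists, to arm).

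**The concern.** The plan guards against knowledge of visit in a reliability sub-study and in an exploratory motility review, but says nothing about it for the reading that supplies the primary endpoint.

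That reading involves judgement, since the reader picks a well-distended stretch of ileum and three places on it. There is also an expected direction: section 2.1 lists bowel wall thickening among the theories of intussusception, and the hypothesis in section 3.2 is that vaccination affects the anatomy of the small intestine. A reader who knows which scan is post-vaccination could, without intending to, measure it slightly thicker.

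All four arms are vaccinated, so the within-arm test is the planned test of change after vaccination. A reading shift would enter it directly. It would also enter the summaries in section 10.3 a) ("Descriptive statistics will be calculated for the entire study population, as well as for each vaccine group at each time point") and any pre/post effect size carried forward under the Power paragraph ("Effect sizes will be reported from the results, to aid in the development of future studies").

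**Working it through.** **Step 1. Who is masked to what.** The plan states no figure to reproduce here, so the first check sets the texts side by side.

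| Reading | Reader | Masked to arm or vaccine type | Masked to time point |
|---|---|---|---|
| MRI wall thickness, all infants (primary) | First radiologist | Yes (4.1, 10.1) | Not stated |
| MRI anatomy, random subset | Second radiologist | Yes (4.1, 10.1) | Yes (9.13) |
| Qualitative motility movies (exploratory) | Both radiologists and a gastroenterologist | Yes for the radiologists (10.1) | Time points randomised (9.13) |
| Ultrasound anatomy, all infants | First radiologist | Yes (4.1, 10.1) | Not stated |
| Ultrasound anatomy, random subset | Second radiologist | Yes (4.1, 10.1) | Yes (9.22) |

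Masking to arm does not imply masking to visit. In every arm the Visit 1 scan precedes vaccination and the Visit 2 scan follows it, so a reader who knows nothing about arm can still know which scan is which.

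**Step 2. Where a reading shift goes.** For arm k let δ_k be the true mean change, b_k the post-minus-pre reading shift and σ the SD of the change.

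- The within-arm mean change estimates δ_k + b_k. The two terms cannot be separated.
- The difference between arms j and k estimates (δ_j − δ_k) + (b_j − b_k). The shift drops out only if b_j = b_k.

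**Step 3. Illustrative size.** Inputs from the documents:

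- a ceiling of 150 infants (4.1) allocated 1:1:1:1 (4.4), so 150/4 = 37.5 per arm on average;
- the benchmark of 70% completing both MRIs (Appendix 2), so 0.70 × 37.5 = 26.25 pairs per arm.

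The documents give no SD, reading shift or alpha. I assume δ = 0, a two-sided 5% test, and b/σ = 0.10, 0.25 or 0.50.

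*Paired t-test in one arm.* The statistic is noncentral t with n − 1 df and noncentrality (b/σ)√n. For n = 37.5 and b/σ = 0.25 the noncentrality is 0.25 × √37.5 = 1.53 and the rejection probability is 0.320.

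*Between-arm F-test on change scores.* The noncentrality is n Σ(b_k − b̄)²/σ², with 3 and 4n − 4 df. If the shift is equal in all four arms this is zero and the test rejects in 5%. If the shift is present in only two arms, each deviation from b̄ is b/2, so the sum is 4 × (b/2)² = b² and the noncentrality is n(b/σ)². For n = 37.5 and b/σ = 0.25 that is 37.5 × 0.0625 = 2.34, and the rejection probability is 0.215.

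| Probability of rejecting with no true change | n per arm | shift 0.10 | shift 0.25 | shift 0.50 |
|---|---|---|---|---|
| Paired t-test, one arm | 37.5 | 0.092 | 0.320 | 0.846 |
| Paired t-test, one arm | 26.25 | 0.078 | 0.234 | 0.693 |
| F-test, equal shift in four arms | either | 0.050 | 0.050 | 0.050 |
| F-test, shift in two of four arms | 37.5 | 0.072 | 0.215 | 0.718 |
| F-test, shift in two of four arms | 26.25 | 0.065 | 0.159 | 0.541 |

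For the paired test, whole-number arms of 37 and 26 give 0.091/0.316/0.841 and 0.078/0.232/0.688, within one percentage point of the table. A simulation of 20,000 trials with arms of 37 or 26 agrees: 0.093/0.314/0.843 and 0.080/0.234/0.688 for the paired test, 0.047 to 0.051 for the F-test with an equal shift, and 0.068/0.211/0.712 and 0.063/0.160/0.532 with the shift in two arms.

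**The case against.** **The plan is silent; it does not unmask the reader.** Nothing says the first reader sees visit labels or reads in visit order. That is right, and it limits the claim to a missing specification. But sections that mask one reader expressly and pass over the other do not commit the first reader to anything.

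**The randomised contrast is protected.** An equal shift cancels in the between-arm change score. This stands while arm masking holds. One point weakens it: a sentence in section 4.1 says that people masked to vaccine type will be told about the other vaccines given, and it is unclear whether this means parents only or imaging staff too. On the wider reading it conflicts with section 10.1 and would split the arms two and two, which is the last case in the table.

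**The within-arm test cannot attribute change to vaccine anyway.** With no unvaccinated arm, other changes between Day 0 and Day 5 remain even under perfect masking. This also stands. Masking removes reading bias only, but that is the part that can be removed without redesign.

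**The shifts have no anchor.** They are assumptions, and the result depends on which is chosen. Simple randomisation does not assure equal arms, and 150 is a ceiling. The table shows how the tests respond to a shift; it does not predict what this trial would show.

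**The masked second read is a safeguard.** It is a partial one. It covers only a subset, its stated purpose is reliability, and no rule lets it correct or replace the first reading.

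**It is a pilot with no power calculation.** That lowers the stakes, but its effect sizes are meant to inform later studies.

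**Conclusion.** The concern holds. The plan specifies time-point masking for the reliability reader and not for the reader who produces the primary endpoint, and no other passage supplies it. Ultrasound has the same gap, with less consequence.

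The exposure is mainly in the four within-arm paired tests and the pre/post summaries. Under the assumptions above, a single-arm test at a nominal 5% would reject in about 8% to 85% of trials across the shifts and arm sizes shown. The between-arm test keeps its 5% level if the shift is common to all arms. Confidence is high that the specification is missing. The documents do not show that the reader would in fact know the visit, or that a shift would occur. It should be fixed; it does not invalidate the design.

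**What to change.** In sections 9.13 and 9.22, state that the primary reader makes the endpoint measurements after both scans have been acquired, from images stripped of visit and date, in random order, masked to time point and arm. Leave the prompt review for clinically concerning findings in section 6.6 as planned, and state that it is separate from the masked endpoint read.

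The plan does not say whether the radiologist who reports concerning findings is also the endpoint reader. If so, that person will have seen the scans as they arrived, and removing labels later masks less completely. The sponsor should say who does each task. Section 4.1 should also be reconciled with section 10.1 on whether imaging staff learn of the other vaccines given.

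The cost is one sentence in each of 9.13 and 9.22, some file preparation, and a wait for the Day 5 scan before the endpoint is measured. Time points are already to be randomised for the motility movies, so the task is a familiar one. No extra scan is needed. If one person now holds both roles, dividing them may call for some rearrangement among the radiologists.

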### 9.2 Ultrasound Imaging

#### 9.21 Methods

Anatomic imaging of the terminal ileum will be done by ultrasound by an ultrasound technologist.

#### 9.22 Image Interpretation

**Anatomic imaging** will be assessed by a pediatric radiologist with expertise in abdominal imaging ([name]). The well-distended distal/terminal ileum bowel and cecum wall thickness will be measured in 3

locations, and a mean wall thickness value will be obtained on each exam. The largest right lower quadrant mesenteric lymph nodes will be measured in short axis on each exam. Any secondary signs of inflammation (perienteric fat stranding, engorged vasa recta, free fluid) will be documented on each exam.

After completion of the primary anatomic review, a second pediatric radiologist with expertise in abdominal imaging will perform the same review on a random subset of subjects in order to determine inter-reader reliability. The second reviewer will be blinded to the initial assessment as well as to the time point of imaging.

## **10 RANDOMIZATION, DATA MANAGEMENT, STATISTICAL PLAN**

### **10.1 Randomization Plan**

Upon meeting the inclusion and exclusion criteria, subjects will be randomized to one of the four vaccine groups: 1) RV1 alone, 2) RV5 alone, 3) RV1 with routine immunizations (DTaP, Hib, PCV13, HBV and IPV) or 4) RV5 with routine immunizations. This will be a simple randomization using SAS® PROC PLAN, which uses a random number generator to make assignments. Study statisticians will generate the assignments in advance of any enrollment. After obtaining informed consent, an unblinded research personnel will contact the statistician to obtain a specific subject's assignment. Parents and all study radiologists will be blinded as to which arm the child is randomized to until completion of the study. Parents will learn which rotavirus the child received at the completion of Visit 3. Parents will be informed about the specific other vaccines used in the study. If there is an urgent medical need to unblind during the study, then this can be done by calling the on call study staff.

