## **4 Research Plan**

### **4.1 Overview of Study**

This study is a prospective clinical study designed to 1) examine the effects of RV1 and RV5 alone or with other routine immunizations on gastrointestinal anatomy 2) to assess the feasibility of conducting a larger scale study. Exploratory objectives include 1) to examine the effects of RV1 and RV5 with or without other routine immunizations on gastrointestinal motility 2) to examine the effects of RV1 and RV5 with or without other routine immunizations on blood and stool cytokines and inflammatory responses, including clinical reactogenicity events 3) to assess patterns and level of vaccine virus shedding after RV1 and RV5 4) to provide preliminary data assessing associations with the pattern of rotavirus vaccine strain (RV1 and RV5) shedding in the stool and blood, stool cytokine responses, and the anatomy and/or functional motility of the small intestine; and examine other factors such as maternal antibody, breast milk antibody, and human blood group antigens to see if these factors modify these responses and 5) to compare MRI and ultrasound imaging.

Healthy infants 6-13 weeks of age will be randomized (1:1:1:1) to receive either, RV1 alone, RV5 alone, RV1 with ACIP routinely recommended immunizations (Diphtheria, Tetanus and Pertussis (DTaP), *Haemophilus influenzae* type b (Hib), pneumococcal conjugate (PCV13), Hepatitis B (HBV) and

inactivated polio (IPV)) or RV5 with routine immunizations. Imaging study personnel and parents will be blinded to the rotavirus vaccine type; parents will be informed about the rotavirus vaccine type at the completion of the study. Up to 150 infants will be enrolled (see inclusion/exclusion below). The age-group of infants 6-13 weeks of age was chosen so enrolled infants can receive their first dose of rotavirus vaccine at the AAP/ACIP recommended age of 2 months (minimum age of 6 weeks and maximum age of 14 weeks and 6 days) and, to assure that other ACIP recommended vaccines can be administered at the recommended age.

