#### **4.4 Randomization and Study Withdrawal**

##### **Randomization Procedures**

The randomization code will be prepared by statisticians in the Epidemiology and Biostatistics Core at CCHMC. The randomization code will link to the vaccine assignment. The subject will be assigned a randomization code. Randomization will take place prior to the vaccine administration, but after the parent/legal guardian has given permission/informed consent, signed the IRB-approved consent form and met all of the inclusion and none of the exclusion criteria. Infants will be randomized 1:1:1:1 to one of four groups: 1) RV1 alone, 2) RV5 alone, 3) RV1 with routine immunizations (DTaP, Hib, PCV13, HBV and IPV or 4) RV5 with routine immunizations.

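### Simple randomization gives 1:1:1:1 only in expectation; concealed blocks of varying size would protect arm balance at small cost

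*Combined protocol and SAP*

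**What the plan says.** Section 10.1 (Randomization Plan) names the method: "This will be a simple randomization using SAS". On the list it says "Study statisticians will generate the assignments in advance of any enrollment", and on release, which follows consent, "an unblinded research personnel will contact the statistician to obtain" the assignment for each infant. No block size, stratum or limit on arm size appears there or elsewhere.

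The ratio is stated twice: "Infants will be randomized 1:1:1:1 to one of four groups" (4.4, Randomization Procedures) and "will be randomized (1:1:1:1) to receive either" one of the four regimens (4.1). The total is a ceiling: "Up to 150 infants will be enrolled" (4.1). Under Power, "no power calculations were conducted".

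The analysis works arm by arm. Section 10.3(b) plans a paired test within each arm and a four-group linear model, possibly "followed by pairwise comparison between groups (6-comparisons") by two-sample t-test. It also plans modifier subgroups, and correlations between shedding and imaging calculated in each arm.

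**The concern.** Simple randomization assigns each infant independently, so chance alone decides how many infants each arm holds. With four arms and at most 150 infants, chance differences are large relative to an average arm of 37.5. Because the final number is open, no planned stopping point restores balance.

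What is at stake is precision. A two-sample comparison is governed mainly by its smaller arm, and the within-arm tests, modifier subgroups and arm-wise correlations all weaken in an arm that happens to be small. The pilot is meant to report effect sizes for planning later studies, so the precision of each arm's estimate matters even without a power target.

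**Working it through.** **Inputs from the documents.** Four arms at 1:1:1:1 (4.1, 4.4); N up to 150 (4.1); simple randomization (10.1); pairwise two-sample tests (10.3(b)); a benchmark of at least 70% of infants completing both MRIs (Appendix 2). There is no sample-size or power figure to reproduce.

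**Assumptions.** Simple is read as independent assignment with probability 1/4 per arm. N = 100 stands for lower enrolment. MRI completion of 70% is taken as independent of arm.

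**Step 1: size of one arm.** Under the binomial model the mean is N/4 and the SD is √(N × 1/4 × 3/4). At N = 150 the mean is 37.5 and the SD is √28.125 = 5.3. The exact binomial 95% range is 27 to 48.

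**Step 2: gap between largest and smallest arm** (500,000 simulated multinomial lists).

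| N | Mean gap | Chance of gap ≥ 10 | Chance that largest/smallest ≥ 1.5 |
|---|---|---|---|
| 150 | 12.6 | 69% | 32% |
| 100 | 10.3 | 54% | 51% |

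At N = 150 the median gap is 12, the smallest arm averages 31.3, and its 5th percentile is 26. A gap of 1 or less has a chance of about 0.3%.

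**Step 3: cost to a given pairwise comparison.** With arms of size a and b, the variance relative to equal arms is (1/a + 1/b) ÷ (8/N). For example, an arm of 27 against one of 37.5 at N = 150 gives (0.03704 + 0.02667) ÷ 0.05333 = 1.19, a 19% loss. Over the simulated lists, for a pair of arms named in advance:

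| N | Mean inflation | 95th percentile |
|---|---|---|
| 150 | 2.1% | 17.6% |
| 100 | 3.2% | 23.8% |

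As an illustration, take a standardised difference of 0.647, chosen to give 80% power at 37.5 per arm (two-sided 0.05, assumed). Under simple randomization, power for a given pair averages 79.2%, with a 2.5th percentile of 72.0%. For RV1 against RV5 with the routine-vaccine arms pooled, the mean variance loss is only 0.7%.

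**Step 4: permuted blocks.** With blocks of 4 the gap is 0 at N = 148 and 1 at N = 150 (38/38/37/37). With blocks of 8, or 4 and 8 mixed, it is at most 2.

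**Step 5: infants analysed.** At N = 150 and 70% with both MRIs, about 105 infants remain. The mean gap among them is about 10.5 with simple randomization and about 6 with blocks. The 5th percentile of the smallest analysed arm is 16 and 20 respectively.

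**The case against.** **The ratio is met.** This stands. Sections 4.1 and 4.4 say how infants will be randomized, not that the arms will end up equal, and 150 does not divide by four. A reader might infer that 10.1 contradicts them; it does not. Nor is there bias, since each infant has the same chance of each arm whatever the list turns out to be.

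**The average loss is small.** This also stands: about 2% in variance, or less than one point of power in the illustration. Blocks insure against an unlucky list. A reader might also infer that all six pairwise tests hang on the smallest arms, but the smallest arm enters only three of them, and the comparison of the two largest arms gains from the imbalance.

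**Blocks have a cost.** True, and somewhat more so here. Section 5.3 has parents told whether the infant receives routine vaccines or rotavirus vaccine alone, and unblinded staff obtain assignments one by one. Someone who knew that blocks were fixed at 4 could foresee 25% of full assignments, or 33% of the alone/routine split; with fixed blocks of 8 the figures are 14% and 20%. Under simple randomization both are 0%. Those figures assume a known, fixed size. Varying and concealing it lowers the risk without removing it.

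**Blocks balance those randomized, not those analysed.** This stands as a limit on the benefit. Missing scans reopen part of the gap (Step 5). Section 4.4 also provides for replacing withdrawn infants and those who vomit soon after the vaccine, without naming the arm that a replacement enters.

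**Calendar time.** It is tempting to add that chance imbalance over time would matter while the imaging is being learned. The documents do not support this. Sections 6.6, 9.13 and 9.22 specify trained technicians and expert radiologists. The novel software is for motility, an exploratory objective. The primary comparison uses each infant's own change over about five days, which largely removes slow drift.

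**Conclusion.** The concern holds as a minor point of precision. At 150 infants, simple randomization produces an expected gap of about 13 between the largest and smallest arm and a 69% chance of 10 or more. The usual cost to a pairwise comparison is about 2% in variance, with a tail of about 18% or more in 5% of lists; at 100 infants these are about 3% and 24%. The plan breaches nothing it states, and no result would be biased.

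The figures rest on reading simple as independent equal-probability assignment. The analysed-set figures rest also on 70% MRI completion unrelated to arm. The documents give no alpha, effect size or power target, so the power figures are illustrative. Severity is minor because this is a pilot of predetermined size.

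**What to change.** In 10.1, replace simple randomization with permuted blocks of randomly varying size (for example 4 and 8). Keep the block sizes out of documents that recruiting and clinic staff can see. Leave the list with the statistician, released one infant at a time after consent, as already planned. In 4.4 or 10.1, add one sentence on how a replacement infant is assigned to an arm.

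The cost is a few lines of code and a short text change before enrolment, plus slight predictability at block ends, which concealment and varying sizes limit. The gap among those randomized falls to about 0 to 2. Under the 70% assumption, the mean gap among those analysed falls from about 10.5 to about 6.
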